### 4.4 Sample size calculation

Targeting a desired sensitivity of 95%, 200 true events allow estimation of sensitivity with precision (expressed as expected width of the 95% confidence interval) of +/- 3%, which is considered adequate. As for specificity, a substantially larger number of “non-events” can be sampled, precision for estimating specificity will be larger.

In this study, we will primarily collect data of induced circulatory arrest, obtained during controlled settings with appropriate reference standards (ECG and (invasive) blood pressure measurements). To collect a sufficient amount of PPG data with true events, the

sample size will be 276 patients consisting of an estimated number of n=200 TAVR-patients (event rate 1/1), n=20 ICD-patients (event rate 1/1) and n=56 VT-ablation patients (event rate 1/3). In case ventricular fibrillation induction or rapid ventricular pacing is not performed or does not result in complete circulatory arrest (as determined on (invasive) blood pressure measurements), the number of patients included will be increased to guarantee the anticipated number of true events, with a maximum of 80 additional patients. Data of the patients without induced circulatory arrest will be used as non-cardiac arrest data.

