## 10. STATISTICAL ANALYSIS

Categorical data will be presented as numbers (percentages) and compared using Chi-square test or Fisher's exact test. Continuous data will be assessed for normal distribution and presented as means  $\pm$  standard deviations or medians (interquartile ranges) whichever appropriate. Comparisons will be performed using the Student's t-test or Mann-Whitney U test, whichever appropriate.

For each patient studied, circulatory arrest data (case data) and non-circulatory arrest data (control data) will be collected. The data obtained will be analysed and used for algorithm development at regular intervals: after inclusion of the first 50 patients with at least one circulatory arrest and afterwards after inclusions of another 50 patients. This enables improvement and refinement of the initial algorithm to gain optimal performance. The first iteration provides a first version of the diagnostic algorithm. The second and third iteration will be used to optimize the algorithm. The fourth iteration will be used as final evaluation of the performance of the algorithm (internal validation). All non-circulatory arrest data will be analyzed for false positive circulatory arrest alarms.

As the algorithm will primarily be developed and validated on non-physiologic circulatory arrest induction using rapid ventricular pacing with aortic balloon inflation during transcatheter aortic valve implantation, a second (external) validation will be performed on data of patients with induced shockable cardiac arrest (i.e. induction of ventricular fibrillation or tachycardias). This most closely resembles clinical sudden cardiac arrest. The final cohort of 50 inclusions with at least one induced event, consisting only of patients who underwent VT ablation or VF induction after s-ICD implantation, will be used for this analysis.

The performance of the PPG-based algorithm will be assessed by calculating the sensitivity, specificity, and positive predictive value with 95% confidence intervals. The specificity is reported based on 1-minute intervals of pulsatile PPG signal correctly identified as non-circulatory arrest. Reporting will follow the recommendations of the STARD guidelines for studies on diagnostic accuracy. Statistical analyses will be performed using SPSS (IBM, Armonk, USA).

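### Specificity is counted in repeated minutes per patient and its precision argued from their raw number, so 95% CIs will be too narrow unless clustered by patient

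*Protocol*

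**What the plan says.** Section 10 (Statistical Analysis) measures performance by "calculating the sensitivity, specificity, and positive predictive value with 95% confidence intervals". It names no interval method. The unit for specificity is a one-minute stretch of pulsatile signal classified as not being an arrest. Section 8.3 has the wristband recording throughout the procedure in all three patient groups, so one patient yields many such units.

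Section 4.4 (Sample size calculation) states: "Targeting a desired sensitivity of 95%, 200 true events allow estimation of sensitivity with precision", with that precision "expressed as expected width of the 95% confidence interval) of +/- 3%, which is considered adequate". It continues: "As for specificity, a substantially larger number of “non-events” can be sampled, precision for estimating specificity will be larger". It plans 200 TAVR patients at an event rate of 1/1, plus "n=20 ICD-patients (event rate 1/1) and n=56 VT-ablation patients (event rate 1/3", 276 patients in all.

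Section 10 takes both arrest and non-arrest data from each patient. The first analysis comes "after inclusion of the first 50 patients with at least one circulatory arrest", so a patient may contribute more than one arrest. The internal validation (fourth iteration) and the external validation each rest on about 50 patients with an event. Neither section mentions within-patient correlation.

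**The concern.** Minutes recorded from one wrist share the fit of the band, the skin, the perfusion and the sources of noise. If these drive false alarms, some patients will produce many and most will produce few or none. A binomial interval on the total number of minutes then claims more information than was collected.

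Section 4.4 reasons in the same way: it ties the precision of specificity to the number of non-events, not to the number of patients. False positive alarms are part of the main endpoint (Section 8.1.1), and sources of noise and of false alarms are secondary endpoints (Section 8.1.2). The question matters most in the two validation sets of about 50 patients, where overstated certainty would be hardest to see.

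**Working it through.** **Inputs from the protocol:** target sensitivity 95%; 200 true events; stated precision of 3 points either way; 276 patients; event rates 1/1, 1/1 and 1/3; validation sets of about 50 patients; one-minute unit for specificity.

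**Assumptions (not in the protocol):** control minutes per patient (60, 90 or 120), ICC (0.01 to 0.30), true specificity 99%, arrests per patient (1 to 3).

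**1. The plan's own figure.** Half-width = 1.96 × √(0.95 × 0.05 / 200) = 3.02 points. Exactly 3 points would need 1.96² × 0.0475 / 0.03² = 203 events. The stated figure reproduces as a plain binomial with independent events.

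**2. Events per patient.** 200 + 20 + 56/3 = about 239 expected events, roughly one per patient who has an event. Independence is therefore a fair planning model for sensitivity.

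**3. Specificity in one validation set.** With m minutes per patient, the design effect is DE = 1 + (m − 1) × ICC, the effective n is (patients × m) / DE, and the half-width grows by √DE. For 50 patients with 90 minutes each, the nominal n is 4,500:

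| ICC | DE | Effective n | Half-width (points) | Ratio |
|---|---|---|---|---|
| 0 | 1 | 4,500 | 0.29 | 1.0 |
| 0.01 | 1.89 | 2,381 | 0.40 | 1.4 |
| 0.05 | 5.45 | 826 | 0.68 | 2.3 |
| 0.10 | 9.90 | 455 | 0.91 | 3.1 |

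For example, at ICC 0.10: 1.96 × √(0.99 × 0.01 / 455) = 0.91 points.

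**4. All 276 patients, 60 minutes each** (16,560 intervals). The naive half-width is 0.15 points. With ICC 0.01, 0.05, 0.10 and 0.30 it is 0.19, 0.30, 0.40 and 0.65 points, or 1.3, 2.0, 2.6 and 4.3 times as wide. At 120 minutes the factors are 1.5, 2.6, 3.6 and 6.1.

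**5. Does precision grow with minutes?** At ICC 0.10, doubling from 60 to 120 minutes raises the effective n for 276 patients from 2,400 to 2,567, about 7% more information for twice the data. As m grows, a patient's effective contribution approaches 1/ICC, here 10 minutes.

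**6. Coverage.** Beta-binomial data were simulated (4,000 runs, specificity 99%, 60 minutes, 276 patients). A naive 95% Wilson interval covers the truth in about 88%, 67%, 53% and 35% of runs at ICC 0.01, 0.05, 0.10 and 0.30. With 50 patients, a plain cluster-robust normal interval covers in about 92.5%, 88.7%, 83.7% and 71.5%. That is better than the naive interval but still short of 95%.

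**7. Sensitivity with 200 events.** One arrest per patient: 3.02 points, unchanged. Two per patient: DE = 1 + 1 × 0.3 = 1.3 at ICC 0.3, giving 3.44 points. Three per patient: 3.82 points at ICC 0.3 and 4.27 at ICC 0.5.

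**The case against.** A reader might infer three stronger points. The protocol supports none of them.

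*The plan computes its intervals as if units were independent.* Section 10 does not say so; it names no method. A statistical analysis plan, not available here, may specify one, and silence on a method commonly left to that plan is no fault in itself. What stands is narrower: the protocol itself fixes a repeated-measures unit and argues precision from its raw count, and the only precision calculation it shows is a plain binomial.

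*The Section 4.4 comparison is false.* It is not. Even at an ICC of 1 with equal recording lengths, 276 patients give an effective n of 276, above 200: at 95% the half-widths are 2.57 and 3.02 points. In the 50-patient example at ICC 0.10 the effective n is 455, and 0.91 points is still well inside 3.02. Section 4.4 gives no figure for specificity, so no stated number is wrong. Only the reasoning fails.

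*The 3-point precision for sensitivity is undermined.* The planned rates amount to about one event per patient, and the wording about at least one arrest is a counting threshold, not a plan for repeats. The effect is nil to modest.

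It is also fair to say that specificity and PPV are secondary, that no threshold or decision rule depends on interval width, and that the protocol offers no evidence that false alarms cluster. This limits the weight of the point. It does not remove it, because false alarms are part of the main endpoint and an ICC of only 0.01 already widens the interval by a factor of 1.3 to 1.5 over the recording lengths considered.

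**Conclusion.** The point holds in conditional form. Ordinary binomial 95% CIs for specificity will be too narrow unless the patient is treated as the cluster; the same applies to PPV and the false-alarm rate if alarms repeat within a patient. For ICC 0.01 to 0.10 the correct interval is about 1.4 to 3.1 times as wide in a 50-patient set with 90 minutes each. At 60 minutes and ICC up to 0.30 the factor is 1.3 to 4.3. In absolute terms, at 99% specificity, the half-width stays below 1 point for ICC up to 0.10. These sizes rest on assumed recording lengths, ICC and specificity.

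Sensitivity changes only where patients contribute several arrests. Section 4.4 is right in direction, but precision is limited by the number of patients and does not simply grow with the number of minutes. This is a change that should be made; it does not threaten the design.

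**What to change.** In Section 10, add wording such as: *The 95% confidence intervals for specificity, positive predictive value and false-alarm rate, and for sensitivity where a patient has more than one arrest, treat the patient as the cluster. They are obtained by a patient-level bootstrap or by GEE with a small-sample-corrected variance. Where the observed proportion is at or near 0 or 100%, an exact or Wilson-type interval on the effective sample size is used.*

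The small-sample correction is needed because plain robust variance under-covers with about 50 clusters. The last sentence is needed because a bootstrap interval has zero width when every unit is classified correctly. The ICC used in that case should be fixed in advance, since such data cannot supply it.

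In Section 4.4, replace the specificity sentence with one that states the number of patients, the expected minutes per patient and an assumed within-patient correlation, and gives the resulting half-width over a range of that correlation.

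The cost is a few lines of text, slightly more analysis work and wider reported intervals. No additional patients or data are needed.

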## SUMMARY

**Rationale:** Out-of-hospital cardiac arrest (OHCA) is a leading cause of global mortality. Delays to initiation of cardiopulmonary resuscitation (CPR) should be as short as possible to achieve the highest survival chance. To reduce treatment delays automated cardiac arrest detection and call for help would be ideal. Photoplethysmography (PPG) is an optical technique often used in sport/smartwatches to monitor heart rhythm at the skin and based on previous studies it seems to have potential to detect circulatory arrest.

**Objective:** To study photoplethysmography signals during 1) induced circulatory arrest; 2) cardiac rhythms without circulatory arrest, and to construct a PPG-based algorithm for circulatory arrest detection.

**Study design:** Prospective multicenter observational study.

**Study population:** 1) Patients scheduled for defibrillation testing after (subcutaneous) implantable cardioverter defibrillator (ICD) implantation; 2) Patients undergoing transcatheter aortic valve replacement (TAVR) with intended rapid ventricular pacing; 3) Patients undergoing ventricular tachycardia ablation.

**Intervention:** Patients will be equipped with a wristband with a PPG-sensor to record PPG signals during hospital stay including during induced circulatory arrests. The circulatory arrest inductions are part of routine practice during above-described procedures and are not a study-related intervention. In case this is not routine practice, an arterial line will be inserted as reference standard for circulatory arrest.

**Main study parameters/endpoints:** Primary endpoints: Sensitivity for circulatory arrest and false positive circulatory arrest alarms.. Secondary endpoints: Positive predictive value for circulatory arrest, Specificity for detection of pulsatile PPG signal, PPG-signal characteristics.

**Nature and extent of the burden and risks associated with participation, benefit and group relatedness:** Given the observational nature of this study and the non-invasive comfortable wristband used for PPG signal recording, the medical risk associated with study participation is negligible. Insertion of an arterial line may carry small risks as outlined in this protocol.

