## **8. METHODS**

### **8.1 Study parameters/endpoints**

#### **8.1.1 Main study parameter/endpoint**

- Sensitivity of the developed algorithm for circulatory arrest detection and false positive circulatory arrest alarms.

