#### **8.1.2 Secondary study parameters/endpoints**

- Specificity of the developed circulatory arrest detection algorithm.
- Positive predictive value of the developed algorithm for circulatory arrest detection
- PPG-derived signal characteristics during circulatory and non-circulatory arrest
- Sources of noise
- Sources of false positive alarms

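### Specificity, a secondary endpoint, is computed only on minutes with a pulsatile PPG signal, so its denominator depends on the index test instead of the ECG and blood-pressure reference

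*Protocol*

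**What the plan says.** The protocol describes specificity in two ways.

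- **Restricted to pulsatile signal.** Section 10 says "The specificity is reported based on 1-minute intervals of pulsatile PPG signal correctly identified as non-circulatory arrest". The Summary lists the secondary endpoint as "Specificity for detection of pulsatile PPG signal".
- **Unrestricted.** Section 8.1.2 lists "Specificity of the developed circulatory arrest detection algorithm", and the secondary objectives in Section 2 say the same in substance. Neither mentions pulsatility.

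The reference standard is separate from the PPG. Section 4.4 describes the induced-arrest data as "obtained during controlled settings with appropriate reference standards (ECG and (invasive) blood pressure measurements". The procedure descriptions in Section 8.3 for ICD, TAVR and VT-ablation patients all establish arrest from pressure and ECG recordings.

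False alarms are handled separately and without a restriction. Section 10 says "All non-circulatory arrest data will be analyzed for false positive circulatory arrest alarms", and Section 8.1.1 makes them part of the main endpoint: "Sensitivity of the developed algorithm for circulatory arrest detection and false positive circulatory arrest alarms".

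**The concern.** Specificity is the proportion of reference-negative units that the test calls negative, so the reference standard should decide which units enter the denominator. Section 10 lets a feature of the index signal decide instead. A patient may be circulating by ECG and pressure while the wrist PPG shows no clear pulse, for example through motion, poor contact or weak perfusion. A detector of circulatory arrest built on PPG is most likely to alarm in such a minute, yet the rule as worded leaves that minute out.

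The protocol itself expects difficult minutes. Section 8.1.2 lists noise and the causes of false alarms as secondary parameters, and Section 2 plans to study unstable arrhythmias. Section 4.4 foresees inductions that do not produce complete arrest and uses data from patients without induced arrest as control data.

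Two things are at stake. The reported specificity may look better than the algorithm's performance over all circulating time. It will also not be the complement of the false-positive proportion over all non-arrest data, although a reader would normally assume that it is.

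**Working it through.** **The plan's own figure.** The only precision statement concerns sensitivity. Section 4.4 says "Targeting a desired sensitivity of 95%, 200 true events allow estimation of sensitivity with precision"; the interval meant is a 95% one, and the margin given is 3% either way. The Wald half-width is 1.96 × √(0.95 × 0.05 / 200) = 0.0302, so the 3% is reproduced. This point does not affect it. For specificity, Section 4.4 says only that precision will be better because more non-events can be sampled; it gives no number to reproduce.

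**Effect of the restriction.** Among minutes that the reference classifies as non-arrest, let

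- q = share without a pulsatile PPG,
- f_p = false-positive rate in pulsatile minutes,
- f_n = false-positive rate in the other minutes.

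Then

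- specificity under Section 10 = 1 − f_p,
- specificity over all non-arrest minutes = 1 − [(1 − q) f_p + q f_n],
- difference = q (f_n − f_p).

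The difference is zero if no minute is left out (q = 0) or if f_n = f_p. It is an upward bias whenever f_n exceeds f_p.

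**Inputs.** The protocol gives none of q, f_p or f_n. All values below are assumptions chosen to show a range. With f_p = 0.5%, the Section 10 figure is 99.5% in every cell. Specificity over all non-arrest minutes would be:

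| q | f_n = 10% | f_n = 30% | f_n = 50% |
|---|---|---|---|
| 5% | 99.025% | 98.025% | 97.025% |
| 10% | 98.55% | 96.55% | 94.55% |
| 20% | 97.6% | 93.6% | 89.6% |
| 30% | 96.65% | 90.65% | 84.65% |

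Worked cell, q = 10% and f_n = 30%: the false-positive proportion is 0.9 × 0.005 + 0.1 × 0.30 = 0.0045 + 0.030 = 0.0345, so specificity is 96.55%. Of the false-positive minutes, 0.030 / 0.0345 = 87% lie outside the Section 10 denominator.

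**Sensitivity to the assumptions.** With f_p = 0.1%, q from 5% to 20% and f_n from 2% to 10%:

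- 0.95 × 0.999 + 0.05 × 0.98 = 0.99805,
- 0.80 × 0.999 + 0.20 × 0.90 = 0.9792.

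The false-positive proportion is then 0.195% to 2.08%, about 2 to 21 times the reported 0.1%. That ratio depends heavily on the assumed baseline. With f_p = 0.5%, q = 20% and f_n = 10%, the proportion is 0.8 × 0.005 + 0.2 × 0.10 = 2.4%, only 4.8 times 0.5%.

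**The case against.** The strongest reply is that the difficult minutes are still analysed. Section 10 examines all non-arrest data for false alarms, and those alarms belong to the main endpoint. The restriction on specificity is stated openly in the Summary and in Section 10, so the figure would carry its own label. This reply stands as to importance. A reader might infer that noisy or low-perfusion minutes are dropped from the study and that the false-alarm burden is hidden. The protocol does not support that: those minutes leave one secondary ratio only. The reply does not remove the conflict with Sections 2 and 8.1.2, or the mismatch between 1 − specificity and the main-endpoint false-alarm analysis.

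A second reply is that the word pulsatile is not defined. It might loosely mean the circulating state, since Section 10 otherwise divides the data only into arrest and non-arrest. No passage says that the algorithm itself chooses the minutes, so a reader who concludes that the test picks its own denominator goes further than the text. This also stands in part. But whoever judges pulsatility judges the PPG, and if the loose meaning was intended, the sentence needs rewriting to say so. An SAP, not shown here, may define how uninterpretable intervals are handled, but the protocol has already stated a rule.

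A third reply is that demanding arterial pressure for every minute would create a new selection. This is correct. Section 13.1 lets ICD and VT-ablation patients take part without an arterial line, and Table 1 has the wristband applied at admission, before the line is inserted. The fix has to allow for this.

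**Conclusion.** The point holds for the secondary endpoint of specificity. Taken literally, the Section 10 denominator is conditioned on the index signal, and the protocol gives two different quantities the same name. The expected direction is upward, on the assumption that false alarms are more frequent in non-pulsatile than in pulsatile circulating minutes. That is plausible for a PPG-based arrest detector, but the protocol gives no data on it.

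The size cannot be estimated from the protocol. The range from about 99.0% to 84.7% against a reported 99.5%, and any fold-increase in false alarms, are illustrations under assumed inputs and not findings. Nor can it be said that high specificity is all but guaranteed, because the protocol does not describe how the algorithm will work. The main endpoint and the sample-size statement for sensitivity are unaffected. This should be fixed, but it does not threaten the study's main result.

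**What to change.** Replace the specificity sentence in Section 10 with a definition such as: *Specificity is the proportion of all recorded 1-minute intervals classified as non-circulatory arrest by the available reference (ECG with invasive blood pressure where recorded, otherwise ECG with non-invasive pressure or clinical status), irrespective of PPG quality, in which the algorithm gives no alarm.*

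Keep the pulsatile-only figure as a supplementary result. State how pulsatility is judged and what share of non-arrest minutes the restriction leaves out. Align the Summary and Section 10 with Sections 2 and 8.1.2.

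The cost is a change of wording, a rule for minutes without invasive pressure, and a recalculation on data already recorded. No patient or procedure is affected. The reported specificity will probably be lower, and minutes without invasive pressure rest on a weaker reference, so showing results by type of reference would help. The change is best made before the validation cohorts are analysed, because a denominator altered after the results are seen is open to challenge.

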## **11. ETHICAL CONSIDERATIONS**

### **11.1 Regulation statement**

The study will be conducted according to the principles of the Declaration of Helsinki version 2013 and in accordance with the Medical Research Involving Human Subjects Act (WMO).

### **11.2 Recruitment and consent**

Patients planned for defibrillation testing after ICD implantation, TAVR or VT ablation will be screened. In case of eligibility, patients will be informed in detail regarding the additional data collection related to study participation and wearing of the wristband. This will be performed by one of the investigators or study nurse trained and supervised by the investigator. Written information is provided as well. Patients will get as much time as they need to reflect on whether they will participate or not. Application of the wristband and data collection will follow only after the patient signs the informed consent form.

